6.5 Follow-up Visits (D2, D4, D8, D15, D29, D91, D181)

All participants will return for follow-up visits following vaccination. During these visits, study personnel will:

- Review the participant's current health status.
- Note any changes in health history since the screening visit, including current medication use and vaccination history.
- Collect blood samples for immunological assays.
- Review memory aid until Day 8.
- Record adverse events until Day 29.
- Record serious adverse events until D181.

The visit will last approximately 30 minutes.

Participants will be asked to provide a stool sample on D29 in addition to the above described procedures.

7. Statistical Analysis Plan

This is an exploratory, non-placebo controlled analysis of immune responses obtained from blood samples. This will provide us with descriptive data to analyze immune responses.

Analysis of Primary Endpoint: Magnitude of antibody responses to QIV at 29 days after vaccination in each study group.

Analysis of Secondary Endpoint: Frequency and severity of adverse events until Day 29 and serious adverse events until D181 after vaccination in each study group.

Descriptive analysis, e.g. tables and histograms, will be conducted to present severity of all AEs. The frequency will be tabulated. Ad hoc analyses of correlations of reactogenicity events with innate and adaptive immune responses may be conducted.

The study staff will aim to enroll 30 participants in each of the statin therapy+QIV and QIV alone arms.

8. Data and/or Specimen Banking

Participants will be asked for permission for the principal investigator to keep any remaining (residual) specimens derived from venous blood collection for possible use in future research studies, such as examining additional immunological assessments or testing for antibodies against other viruses or bacteria. Future use samples/specimens will not be sold or used directly for production of any commercial product. These samples/specimens are protocol-required; thus, participants must agree to future use of these samples/specimens as a condition of their study participation.

These samples/specimens will be stored at the Hope Clinic and shipped regularly to [REDACTED] lab at Stanford and other collaborating labs. The de-identified (all personal identifying information of the participant will be removed) samples/specimens will be labeled and stored in freezers at -80°C or in liquid nitrogen tanks.

In keeping with NIH policy on scientific data sharing, gene expression (RNA sequencing) data and immunological assay results will be made publicly available through public database deposition and peer-reviewed publication. Participants will be fully de-identified (i.e., disseminated data will not contain direct identifiable information). Demographic data (e.g., age, race and/or ethnicity, sex/gender) associated with participants will be kept strictly separate from all experimental results, including gene expression data. This practice has become standard to protect participant privacy.

9. Sharing of Results with Participants

Laboratory results

Immunologic assay or omics results will not be reported to participants as these are intended for research purposes only and therefore cannot be reported to patients per Clinical Laboratory Improvement Amendment (CLIA) regulations.

The results from safety laboratory tests conducted prior to statin therapy can be shared with participants.

Incidental findings

Incidental findings that appear in the results of the safety labs drawn will be disclosed and explained to the participant by the study investigator, who will provide a referral to the appropriate clinical specialist and information on how to obtain health insurance to secure treatment if needed. The study investigator will also send a message to the participant's primary care provider requesting follow-up with the participant if the participant authorizes this and provides relevant contact information.

10. Study Timelines

Individuals will participate in this study for a total of 8 months. Recruitment of all participants will require 24 months. The study and data analysis should be concluded within 48 months of start date.

11. Inclusion and Exclusion Criteria

Inclusion Criteria

1. Able to understand and give informed consent.
2. Age 18-50 years.
3. Women of child bearing potential must agree to use effective birth control for the first 3 months of the study. A negative urine pregnancy test must be documented prior to vaccination.

Exclusion Criteria for All Participants

1. History of allergy or serious adverse reaction, including Guillain-Barré syndrome, to a vaccine or vaccine products.
2. History of a medical condition resulting in impaired immunity such as active solid tumors, leukemia, lymphoma, use of immunosuppressive drugs, chemotherapy or radiation therapy. Persons with previous skin cancers or cured non-lymphatic tumors are not excluded from the study.
3. History of HIV, Hepatitis B or Hepatitis C infection.
4. Chronic clinically significant medical problems that could be considered active or unstable (i.e diagnosed within the past 3 months or requiring a change in medication within the past 3 months). This is including (but not limited to):
 - a. Insulin dependent diabetes

- b. Severe heart disease (including arrhythmias)
- c. Severe lung disease
- d. Severe liver disease
- e. Severe kidney disease
- f. Severe hypertension: defined as life-threatening consequences (e.g., malignant hypertension, transient or permanent neurologic deficit).
- 5. BMI > 30
- 6. Current or previous use of statins or any other lipid-lowering drug.
- 7. Pregnancy or breast feeding, or plans to become pregnant in the first 3 months of study participation.
- 8. History of influenza infection within the same influenza season.
- 9. Receipt of blood products or immune globulin product within the prior 3 months.
- 10. History of excessive alcohol consumption, drug use, psychiatric conditions, social conditions or occupational conditions that in the opinion of the investigator would preclude compliance with the trial.
- 11. Receipt of any live vaccines 30 days before, or plans to receive any live vaccines 30 days after vaccination.
- 12. Receipt of any inactivated vaccines 14 days before, or plans to receive any inactivated vaccines 14 days after vaccination.

For participants randomized to the statin therapy+QIV group:

- 1. Participant is currently taking any medication that has known interactions with statin therapy.
- 2. History of renal or hepatic impairment.
- 3. Safety lab results showing:
 - a. CPK \geq 1.5 ULN
 - b. AST \geq 1.5 ULN
 - c. ALT \geq 1.5 ULN
 - d. LDL \geq 160 mg/dL

12. Population

HMG-CoA reductase inhibitors decrease cholesterol synthesis and possibly the synthesis of other biologically active substances derived from cholesterol. This may cause fetal harm when administered to pregnant female. Pregnant women are also excluded from the study as their immune responses after vaccination will differ from the general population.

13. Vulnerable Populations

No vulnerable populations will be enrolled. Specifically, pregnant persons, children, prisoners, and cognitively impaired persons will not be enrolled. Non-English speakers will not be excluded.

14. Local Number of Participants

We anticipate needing to enroll and screen 150 participants locally to identify 30 participants in the statin therapy QIV arm and 30 participants in the QIV alone arm.

15. Recruitment Methods

15.1 Patients will be recruited following IRB approval.

15.2 Participants will be recruited from the general population of metro Atlanta with the methods detailed below.

15.3 Participants may be identified and recruited from past subjects who agreed to be contacted for future studies or by self-referral from IRB approved advertisements from

- postings of IRB-approved flyers in and around the Emory University campuses as well as on electronic notification boards ; posting approved flyers on Emory and partner institution shuttles (e.g., Georgia Tech);
- use of various social media platforms such as Facebook, Twitter, Instagram, and other mobile apps in compliance with Emory policy; Study staff will use the official Emory University Facebook account and Instagram Emory Get Involved account, where IRB approved social media ads will be posted. The potential volunteers fill in their contact information in the “lead document form” provided by Facebook by default. The form collects the potential participant’s basic contact information such as name, best contact phone number and email address etc. Facebook collects the leads and provides it to the recruitment staff, who save the data in a password protected database on the Emory Hope Clinic’s shared drive.
- listservs (such as CDC, Emory University, Emory Vaccine Center, and Vaccine Dinner Club), and clinical trial recruitment websites such as Research Match.org; listing of clinical trials on the Emory clinical trials database (clinicaltrials.emory.edu); contacting past participants from the HIPAA-compliant clinical trials database at the Hope Clinic who have agreed to be contacted for future studies; presentations by Hope Clinic faculty at various University and community venues; and volunteer word-of-mouth (direct referrals).

Study recruiters/coordinators will contact potential volunteers once identified and tell them about the study and see if he/she is interested. If the potential subject is interested, the recruiter will obtain an oral consent and prescreen them for the study using an IRB-approved screening checklist. Qualified subjects will be scheduled to come into the clinic and be fully consented and proceed with screening/enrollment.

16. Withdrawal of Participants

Participants may voluntarily withdraw their consent from all future study activities including follow up at any time without penalty or loss of benefits to which they are otherwise entitled.

Participants may be terminated from the study prior to study completion for reasons that might include, but are not limited to, those listed below. The investigator will inform the participant that all data acquired prior to termination will be included in the study analysis unless participant withdraws consent.

16.1 Participant no longer meets eligibility criteria.

16.2 The participant is considered by the PI to be “lost to follow-up” (i.e., no further followup is possible because attempts to reestablish contact with the subject have failed).

16.3 The participant dies.

16.4 As deemed necessary by the PI or designee for noncompliance of any nature.

16.5 The participant becomes pregnant.

16.6 If the study is prematurely terminated by the sponsor or the investigator for any reason, the investigator will promptly inform the study participants and assure appropriate follow-up, as necessary. The investigator will provide a detailed written explanation of the termination to the IRB.

Participants with early termination status (before Day 8) are replaced as needed to preserve adequate sample size for the primary endpoint analysis.

17. Continuation of treatment

- Following initiation of statin therapy, participants randomized to the statin therapy+QIV group will: Continue receiving the study drug as planned if they experience grade 1 diarrhea or grade 1 elevation in CPK(>ULN - 2.5 x ULN) or LFTs (>ULN - 3.0 x ULN).
- Temporarily halt receipt of statin therapy for three to 7 days and receive a new set of safety labs (CPK; LFTs) if they experience a grade 2 elevation in CPK (>2.5 x ULN - 5 x ULN) or LFTs (>3.0 - 5.0 x ULN) and without alternative etiology. If afterwards the labs are graded 1 or within normal limits, the participant may restart the statin therapy. If the labs do not trend to grade 1, the drug will be halted and the participant will be followed for safety and not vaccination if prior to D1.
- Permanently halt receipt of statin therapy if they experience a grade 3 elevation in CPK (>5 x ULN - 10 x ULN) or LFTs (>5.0 - 20.0 x ULN) after starting ST.
- The same rules apply to diarrhea and myalgias and other symptoms related to statin.

18. Risk to Participants

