Project Design	Longitudinal cohort study in which participants will receive either 8 weeks of statin therapy and a seasonal quadrivalent influenza vaccine (QIV) or a seasonal quadrivalent influenza vaccine (QIV) alone. Immune responses in the blood will be assessed.
Primary Objective	Compare the antibody (Ab) response to QIV in statin recipients and non-recipients.
Secondary Objectives	Assess the safety profile of statin therapy + QIV v/s QIV alone.
Exploratory Objectives	
 Explore the effect of statin therapy on immune signatures after vaccination. Evaluate the effect of statin therapy on plasma cytokine responses to vaccination.
Research Intervention(s)/Interactions	Initiation of 8 weeks of statin therapy and immunization with a single dose of seasonal QIV.
Study Population	Healthy adults (age 18 to 50 years) without history of statin use and without current receipt of seasonal influenza vaccine or recent influenza infection.
Sample Size	N=30 in the Statin + QIV arm. N=30 in the QIV alone arm.
Study Duration for individual participants	8 months.
Study Specific Abbreviations/ Definitions	Ab –antibody QIV – seasonal quadrivalent influenza vaccine
Funding Source	Hope Clinic Internal funds

2. Objectives

Primary Objective:

Compare the antibody (Ab) response to QIV in statin recipients and non-recipients.

Secondary Objective:

Assess the safety profile of statin therapy + QIV v/s QIV alone.

Exploratory Objectives:

1. Explore the effect of statin therapy on innate immune signatures to QIV.
2. Evaluate the effect of statin therapy on plasma cytokine response to QIV.

3. Background

Statins are widely used for their lipid-lowering and cardiovascular protective effects¹. Additional research has shown that statins can be anti-inflammatory, and play a part in modulating the immune system²⁻⁴. These effects are called into action in events such as pneumonia⁵, influenza^{6,7}, and sepsis⁸.

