5.1 Description

Atorvastatin therapy

Atorvastatin is a lipid-lowering agent of the statin family that functions by blocking a rate-limiting enzyme, HMG-CoA reductase, in the lipid metabolism. This agent is commonly used for primary and secondary prevention of dyslipidemia. Participants will be asked to take Atorvastatin 80 mg daily at night, for 4 weeks prior to the vaccination and continue the statin therapy for 4 weeks after vaccination.

The 80mg dose of atorvastatin allows for evaluation of the immunologic effects of statin medication with a short duration of therapy prior to vaccination. Studies have shown that 80mg of atorvastatin for 1 month affects inflammatory responses while lower doses of statin for longer periods may not. The 80mg dose reduced inflammation related to including NF- κ B while other studies looking at lower doses of statin for 3 months did not find a difference in NF- κ B¹⁹. Observational studies have investigated the dose-response question for statin therapy and vaccine effect but they either had insufficient sample size for that question²⁰ or there was a trend toward lower vaccine efficacy with higher dose statin, though this was not statistically significant²¹.

Quadrivalent seasonal influenza vaccine

The FDA-approved quadrivalent seasonal influenza vaccine contains four distinct strains: two influenza A viruses and two influenza B viruses. The approved seasonal QIV will be purchased from the manufacturer to be given for each season of influenza.

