6.1 Screening and Consenting (D-60 to D-32)

6.1.1 Potential participants interested in the study will respond to study ads. Recruiters from the Hope Clinic will then contact them for a telephone screening, during which the research study will be explained in lay terms and eligibility criteria will be reviewed. If all eligibility criteria are met and the participant remains interested, an in-person screening appointment will be scheduled. Prior participants in other studies conducted at the Hope Clinic, and who had indicated their willingness to participate in other studies may also be contacted for a telephone screening visit.

6.1.2 At the in-person screening appointment , study staff will review the informed consent form with the participant and will answer all questions related to the study. Once the participant signs the informed consent, they will be assigned a unique study participation number. The following procedures will be performed:

- Recording of demographic information and review of medical history including recent influenza infection, including current medication use (medications that may interact with Atorvastatin) and vaccination history (previous receipt of influenza vaccines).
- Vital signs and targeted physical exam as indicated based on review of participant health status.
- A urine pregnancy test will be performed if the participant is a woman of child-bearing potential.
- Blood sample collection for baseline immunological assays and baseline clinical labs. Clinical labs may be repeated at investigator discretion.

6.1.3 Participants who remain eligible for the study will be randomized to either Statin therapy + QIV arm or QIV alone arm. Participants randomized to the Statin therapy+ QIV arm will receive the Atorvastatin pills with clear instructions on how to use them in a separate visit.

6.1.4 Clinical staff wil provide participants with a stool collection kit along with an information sheet explaining how the stool collection is done. The steps will be explained to the participant who will be asked to provide a stool sample on D-31, D1, and D29.

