6.2 Initiation of Statin therapy (D-31 to D-29)

Participants randomized to the Statin + QIV arm will be asked to come back to the Hope Clinic for an extra visit one month prior to date of vaccination. The following procedures will be performed:

- Review of interim medical history for any updates or changes.
- Review of concomitant medications for any updates or changes.
- Recording of vital signs and targeted physical exam if indicated.
- Blood sample collection.
- Stool sample collection.
- Re-verification of eligibility criteria.
- Completion of prescription form by licenced provider and dispension of Atorvastatin 80mg by the pharmacy at the clinic.
- Distribution of the drug to participant by study coordinator or nurse or provider with clear instructions on modalities of administration of the drug and common side-effects.

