6.4 Vaccination Visit (D1)

The following actions will be performed on the day of vaccination:

- Review of inclusion and exclusion criteria to confirm eligibility.
- Review of medical history, concomitant medications and vaccinations.
- Collection of vital signs.
- Completion of a targeted physical exam if needed.
- For participants of child-bearing potential, a negative urine pregnancy test is required.
- For the statin therapy group, participant compliance to the drug will be assessed.
- Blood samples for immunologic assays will be collected prior to vaccination
- Stool sample collection
- Participants will receive the CDC influenza vaccine information sheet and review it prior to vaccination.
- Participants will then receive QIV via the intramuscular route, administered by a clinical research nurse or provider.
- Participants will be observed for a minimum of 15 minutes for any immediate hypersensitivity reactions.
- Participants will be asked to fill a memory aid for 7 days after vaccination. Participants will have the option of an online survey or paper memory aid.

The visit will last approximately 60 minutes.

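### The primary objective compares randomised arms, but Section 7 plans no between-arm estimate or confidence interval and gives the pre-randomisation sample no role

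*Combined protocol and SAP*

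**What the plan says.** Section 2 gives the primary objective as "Compare the antibody (Ab) response to QIV in statin recipients and non-recipients". Section 6.1.3 makes this a randomised comparison: "Participants who remain eligible for the study will be randomized to either Statin therapy + QIV arm or QIV alone arm".

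Section 7 introduces the analysis with "This will provide us with descriptive data to analyze immune responses". Its entire primary entry is "Analysis of Primary Endpoint: Magnitude of antibody responses to QIV at 29 days after vaccination in each study group", which repeats the endpoint in Section 4. The only methods that Section 7 names are tables, histograms and frequencies for adverse events, plus optional ad hoc correlations of reactogenicity with immune responses. Elsewhere, Section 21.3 allows laboratory and demographic data to be linked so that age can be controlled for. That is a data-handling permission and does not mention baseline antibody.

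Three samples precede vaccination:

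- **V1, screening (Section 6.1.2):** "Blood sample collection for baseline immunological assays and baseline clinical labs". Randomisation follows in 6.1.3, and Appendix A lists the immunology draw at V1.
- **V2 (Section 6.2):** "Participants randomized to the Statin + QIV arm will be asked to come back to the Hope Clinic for an extra visit".
- **D1 (Section 6.4):** "Blood samples for immunologic assays will be collected prior to vaccination". By then the statin arm has been on treatment, which Section 5.1 schedules "for 4 weeks prior to the vaccination and continue the statin therapy for 4 weeks after vaccination".

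**The concern.** Describing each arm separately does not answer a comparative objective. The reader would have two summaries and would have to infer the difference and its uncertainty. Section 7 does not even fix the per-arm summary, such as a geometric mean titre by strain.

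Leaving the baseline unspecified has two further consequences. First, at 30 per arm a chance difference in pre-existing antibody passes into an unadjusted Day 29 contrast in proportion to the baseline-to-Day 29 correlation. This is avoidable imprecision, not bias. Second, the choice between V1, D1 and fold-rise could be made after results are seen. A later choice of D1 would adjust for a value measured after about four weeks of statin in one arm only.

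**Working it through.** **There is no plan figure to reproduce.** The documents give 30 per arm with no SD, effect size, alpha or power. Everything below except n is an assumption: two-sided 95% intervals, baseline-to-Day 29 correlation ρ of 0.3 to 0.7, and log2-titre SD of 1.5 (range 1.0 to 2.0).

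**Which sample can serve as baseline.** Section 20 confirms that V2 is for the statin arm only.

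- QIV alone: V1 and seven follow-up visits at $75, plus vaccination at $125, is 8 × 75 + 125 = $725, the stated lower total.
- Statin arm: adding $100 for initiation and $20 for the call gives $845, the stated upper total.

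QIV-alone participants therefore have no V2. D1 is common to the arms but follows statin in one of them. Only V1 is both common and pre-treatment.

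**Precision.**

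- Unadjusted SE = √(2/30) = 0.258 SD. Half-width = t(0.975, 58 df) × 0.258 = 0.517 SD.
- V1-adjusted SE = 0.258 × √(1 − ρ²) × √(1 + 1/56). The last factor is the small-sample cost of one covariate. The half-width uses 57 df.
- Margin on the geometric mean titre ratio = 2^(half-width × 1.5).

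| | Unadjusted | ρ = 0.3 | ρ = 0.5 | ρ = 0.7 |
|---|---|---|---|---|
| √(1 − ρ²) | – | 0.954 | 0.866 | 0.714 |
| 95% half-width (SD) | 0.517 | 0.498 | 0.452 | 0.373 |
| SE reduction | – | 4% | 13% | 28% |
| Ratio margin, log2 SD 1.5 | ×/÷ 1.71 | ×/÷ 1.68 | ×/÷ 1.60 | ×/÷ 1.47 |
| Power for a 0.6 SD effect | 62.8% | 66.0% | 74.4% | 88.7% |

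Without the small-sample factor, adjusted power is 66.8%, 75.1% and 89.2%. For log2 SD of 1.0 and 2.0, the unadjusted margin is ×/÷ 1.43 and ×/÷ 2.05. At ρ = 0.5 the adjusted margin is 2^0.452 = 1.37 and 2^0.904 = 1.87.

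**Chance imbalance.** The SE of the baseline difference is also 0.258 SD, so the probability of an imbalance above 0.3 SD in either direction is 2 × [1 − Φ(0.3/0.258)] = 24.5%. An imbalance of 0.3 SD moves the unadjusted Day 29 difference by 0.3ρ, which is 0.09, 0.15 or 0.21 SD.

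**Season.** Recruitment takes 24 months (Section 10) and vaccine is bought each season (Section 5.1). In a simulation of 8,000 trials with two seasons 0.5 SD apart, the SE fell below the unadjusted value by 3.8/11.4/26.9% with V1 alone and by 5.8/14.4/30.4% with V1 and season. That is a further 2–5%. With no season effect, including season costs about 1%.

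**D1 instead of V1.** Assume correlations with Day 29 of 0.5 for V1 and 0.6 for D1, and 0.85 between V1 and D1. The SE is then 0.226 SD with V1 and 0.208 SD with D1, about 8% smaller. Suppose statin shifts the D1 titre by 0.1 or 0.2 SD and has no true Day 29 effect. The D1-adjusted estimate then moves by about 0.6 × 0.1 = 0.06 or 0.6 × 0.2 = 0.12 SD (simulated: −0.058 and −0.118). The V1-adjusted estimate stays at zero (0.002 and 0.001).

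**The case against.** - **The study is labelled exploratory and descriptive.** It claims no hypothesis or power, so the missing test is deliberate. That stands, and the power figures are illustration only. It does not excuse the lack of an estimated difference with its uncertainty when the stated objective is to compare randomised arms.
- **D1 may be the more natural baseline for response to vaccine.** V1 can precede vaccination by up to 60 days, visits outside the window are allowed, and exposure between V1 and D1 would be missed. If the target is the rise from the moment of vaccination, a statin shift in D1 is arguably not part of it. This has weight, and the SAP should say which effect it targets. But D1 is post-randomisation, and adjusting for it can remove or add part of the treatment effect. It belongs in a sensitivity analysis.
- **The arms may differ by more than chance.** Section 11 lists extra exclusions for those randomised to statin. That is a separate problem. Baseline adjustment does not cause it and would not necessarily cure it.
- **Strain may change between seasons, and four ratios leave no single primary result.** Strain should be read as vaccine component, with season in the model. Reporting and averaging rules need to be fixed in advance.
- **The precision gain rests on assumed correlations, and no titre assay is named at V1.** Both are true. At ρ = 0.3 the gain is small. That affects the value of adjustment, not the need for a between-arm estimate.

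**Conclusion.** The concern holds. Section 7 does not deliver the comparison in the primary objective, and it leaves open the role of a pre-randomisation sample already collected in both arms. The first part follows from the text alone. The size of the second part rests on assumed values. Adjustment for V1 narrows the 95% half-width from 0.52 SD to between 0.50 and 0.37 SD for ρ of 0.3 to 0.7, which is modest at the low end and substantial at the high end. The trial remains interpretable, so this should be fixed but is not fatal. It needs to be settled before outcome data are seen.

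**What to change.** Replace the primary analysis line in Section 7 with wording such as:

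> For each vaccine strain, the difference between randomised arms in log2 Day 29 antibody titre will be estimated with a linear model adjusting for the V1 (pre-randomisation) log2 titre to the same strain and for influenza season. It will be reported as an adjusted geometric mean titre ratio (statin + QIV / QIV alone) with a 95% confidence interval. The same model with the D1 titre in place of V1 is a sensitivity analysis.

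Alongside this, the SAP should state:

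- whether the four strain ratios are reported separately or also averaged (Section 3 cites strain-specific statin effects, a reason to keep them separate);
- how strains are matched across seasons;
- how randomised participants who are not vaccinated (Section 17) or are replaced (Sections 16 and 22.4) are counted, which the wording above does not settle.

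If the readout is not a titre, use the log of that readout.

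The cost is SAP text and one linear model per strain, with no new visit or blood draw. If the laboratory planned antibody assays only from D1, about 60 V1 samples (60 × 4 = 240 strain results) must be added, for little gain if the correlation is near 0.3.

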Appendix A. Schedule of Procedures

	-60 to -32	-31 to -29	1	2	4	8± 1	15 ±2	29± 3	91± 7	181 ±15	Phone call^
	V 1	V2	V3	V4	V5	V6	V7	V8	V9	V10	
Informed consent	x										
Demographics, medical history	x										
Interim medical history		x	x	x	x	x	x	x	x	x	x
Medications	x	x	x	x	x	x	x	x	x	x	x
Targeted physical exam	(x)	(x)	(x)	(x)	(x)	(x)	(x)	(x)	(x)	(x)	
Vital signs	(x)	(x)	(x)	(x)	(x)	(x)	(x)	(x)	(x)	(x)	
Blood draw for screening	x										
Stool Sample collection		x	x					x			
Pregnancy test (if applicable)	x		x	(x)	(x)	(x)	(x)	(x)	(x)	(x)	
Vaccination			x								
Statin therapy*		x	x	x	x	x	x	x			
Memory Aid			x	x	x						
Blood draw for immunological assays	x	x	x	x	x	x	x	x	x	x	
Clinical labs for statin therapy	x		x					x			
Adverse events		x	x	x	x	x	x	x			x
Serious adverse events		x	x	x	x	x	x	x	x	x	

Conducting a visit outside window is allowed at investigator discretion

Parentheses indicate a given procedure will be conducted if relevant for the visit: vital signs and pregnancy testing if applicable will be on the day of screening, prior to statin therapy initiation and prior to vaccination.

*Each participant receiving statin therapy will have clinical labs drawn. The tests conducted will be: Lipid profile, Creatinine Phosphokinase, Liver function tests, CRP. These tests will be valid for 30 days.

[^]phone call is completed 15 days after initiation of statin therapy.

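### Section 11 attaches a second exclusion list (interacting medication, renal or hepatic history, laboratory limits) to the statin arm only; followed as written, it filters one randomised arm on baseline characteristics.

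*Combined protocol and SAP*

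**What the plan says.** Section 11 has two exclusion lists. The first covers all participants. The second is introduced by "For participants randomized to the statin therapy+QIV group" and excludes people who take a drug known to interact with statins, people with a "History of renal or hepatic impairment", and people with CPK, AST or ALT at or above 1.5 x ULN or LDL at or above 160 mg/dL.

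The lists overlap in part. Common item 3 excludes "History of HIV, Hepatitis B or Hepatitis C infection" in both arms. Common item 4 covers "Chronic clinically significant medical problems that could be considered active or unstable", and names severe liver and severe kidney disease (4d, 4e). Common item 6 excludes users of lipid-lowering drugs. The common list has no laboratory limit and no general exclusion for interacting drugs.

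On timing, Section 6.1.2 reviews medication that might interact with atorvastatin at the in-person screening visit and includes "Blood sample collection for baseline immunological assays and baseline clinical labs". Section 6.1.3 follows: "Participants who remain eligible for the study will be randomized to either Statin therapy + QIV arm or QIV alone arm".

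Appendix A marks clinical labs at V1, V3 (D1) and V8 (D29), in a row labelled as being for statin therapy. Its footnote says: "Each participant receiving statin therapy will have clinical labs drawn". Results are valid for 30 days.

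**The concern.** The primary objective is a comparison of antibody response between statin recipients and non-recipients. Randomisation is its main protection, since Section 7 describes the study as not placebo-controlled. An exclusion that takes effect only once a person is known to be in one arm undoes part of that protection.

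Take two people with the same screening history, for example a stable, mild hepatic history or an LDL above the limit. Allocated to statin, the person meets an exclusion criterion. Allocated to vaccine alone, the person does not. Someone who leaves the statin arm before D1 has no Day 29 response, so keeping the data already collected does not bring that person back into the primary comparison. Section 16 (before Day 8) and Section 22.4 (Day 8 or earlier) allow replacement, which restores the number but not the balance. Section 7 names no analysis population and gives no rule for people excluded after randomisation.

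Two further wording points bear on the same list:

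- **Who has V1 labs.** Section 6.1.2 reads as everyone screened; the row label and footnote in Appendix A mention only statin therapy. This is ambiguous rather than contradictory.
- **Whether the entry limits act again on D1.** Section 6.4 reviews the exclusion criteria on D1 and Appendix A marks labs at that visit. Section 17 has study drug continue with CPK up to 2.5 x ULN and LFTs up to 3.0 x ULN. A statin-arm D1 result of 1.5 to 2.5 x ULN (CPK) or 1.5 to 3.0 x ULN (AST, ALT) falls under both texts.

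**Working it through.** The plan gives no figure to reproduce: there is no failure rate by criterion, and 30 per arm comes without a stated effect size, SD or power. The textual check comes first, then a calculation for scale.

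**1. What is one-sided after the overlap**

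| Second-list item | Already excluded in both arms | Left to the statin arm only |
|---|---|---|
| Interacting medication | Lipid-lowering drugs (item 6) | All other interacting drugs |
| Renal or hepatic history | Hepatitis B or C (item 3); severe disease that is active or unstable (4d, 4e) | Milder or stable history |
| CPK, AST, ALT, LDL limits | None | All four limits |

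**2. Whether the text lets the list act after allocation.** It does. The heading is conditional on randomisation. Section 6.2 re-verifies eligibility at V2, a visit described for the statin arm. Section 16.1 makes no longer meeting eligibility a ground for termination, and early terminations may be replaced.

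**3. Size, under stated assumptions.** Let f be the share of otherwise eligible adults who meet only a second-list criterion, and delta the gap in mean response, in SD units, between those who fail and those who pass. Both are assumed. If the statin arm contains only people who pass and the vaccine-alone arm contains both kinds, then

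- bias = (mean of those who pass) − [(1 − f) x (mean of those who pass) + f x (mean of those who fail)], which is f x delta in size;
- chance that at least one of 30 allocated to statin is affected = 1 − (1 − f)^30;
- standard error of the difference with 30 per arm = sqrt(2/30) = 0.258 SD.

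| f | P(at least one of 30) | Bias at delta = 0.5 SD | Bias / standard error |
|---|---|---|---|
| 1% | 26% | 0.005 SD | 0.02 |
| 2% | 45% | 0.010 SD | 0.04 |
| 5% | 79% | 0.025 SD | 0.10 |
| 10% | 96% | 0.050 SD | 0.19 |

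The second column shows how likely the rule is to be used; it does not measure bias. For the bias to reach half a standard error (0.129 SD), delta must be 0.129/0.05 = 2.6 SD at f = 5%, or 0.129/0.10 = 1.3 SD at f = 10%. Gaps that large are unlikely.

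**4. Whether V1 labs can serve for everyone.** V1 runs from D-60 to D-32 (29 days) and V2 from D-31 to D-29 (3 days), giving 29 x 3 = 87 date pairs with gaps of 1 to 31 days. Only D-60 with D-29 (31 days) exceeds the 30-day validity. This counts date pairs and is not a probability. It shows that V1 results would nearly always still hold at V2, where Appendix A schedules no clinical labs.

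**5. Extra screening.** Section 14 plans 150 screens for 60 places, a yield of 60/150 = 40%. Assume this yield reflects the common list only.

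- Current text: (30 + 30/(1 − f))/0.4 = 153.9 at f = 5%, 158.3 at f = 10%.
- List applied to all: (60/(1 − f))/0.4 = 157.9 at f = 5%, 166.7 at f = 10%.
- Difference: 3.9 and 8.3 screens.

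**The case against.** The strongest reply is that the procedures already point to screening everyone. Section 6.1.2 asks about interacting drugs and draws clinical labs before Section 6.1.3 randomises those still eligible. There is little reason to review atorvastatin interactions before allocation unless the answer decides eligibility. On that reading the heading in Section 11 is merely loose. This may well describe practice, but no section says it, and Section 11, which sets eligibility, says something else. If it is the practice, correcting the heading costs almost nothing.

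The second reply is that the bias is small by the calculation above, and Section 7 calls the analysis exploratory and descriptive. This stands. It limits the weight of the point but does not justify keeping a one-arm rule that is easily removed.

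The third is that the change does not equalise everything. V2 re-verification is still described for the statin arm only, and Section 17 can still lead to statin-arm participants going unvaccinated because of on-treatment results. This is correct. The change removes the one-sided baseline screen; losses that arise during treatment are a different matter and lie outside this point.

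Two smaller replies also have force. Section 16 says participants may be terminated, so removal is permitted rather than automatic. And Section 17 opens by referring to the period after statin initiation, so a natural reading is that Section 11 governs entry and Section 17 governs what follows. The D1 eligibility review does not say which reading applies.

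**Conclusion.** The concern holds. As written, the second list is a stated rule that depends on allocation, and its part not covered by the common list can select on baseline characteristics in one arm of the primary comparison.

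Neither the size nor the direction of the bias can be derived from the documents. The range of 0.005 to 0.05 SD rests on assumed values of f (1% to 10%) and delta (0.5 SD), and on the list being applied literally. If staff already apply it to everyone before randomisation, the bias from this source is nil. The point should be fixed because the remedy is cheap and certain, not because a large bias has been shown. Confidence is medium, since actual practice at screening is unknown.

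**What to change.** - **Section 11:** remove the arm-specific heading and apply the second list to all participants, limits unchanged, using V1 history and V1 lab results. State that randomisation waits until those results have been reviewed; Section 6.1 gives the order of draw and randomisation but not when results return.
- **Appendix A:** state that V1 clinical labs are drawn for everyone screened, and align the row label and footnote.
- **Sections 11, 6.4 and 17:** reconcile whether the entry lab limits act again on D1. This review takes no position on which rule should govern.

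Cost: a wording amendment if V1 labs are already drawn for everyone, as Section 6.1.2 suggests; otherwise one set of V1 labs for each person screened who would not now have them. Expect about 4 (f = 5%) to 8 (f = 10%) more screens than the current text would need. Some people who would have received only the vaccine will be excluded on statin-related grounds, so the result will apply to statin-eligible adults, a narrower group than the healthy adults named in the study summary.
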